2.2.3 Withdrawal of Informed Consent

Any data collected in the clinical database after a patient withdraws informed consent from all further participation in the trial, will not be included in the analysis. The date on which a patient withdraws full consent is recorded in the eCRF.

Additional data for which there is a separate informed consent, e.g., PK, [REDACTED] etc., collected in the clinical database without having obtained that consent will not be included in the analysis. These data will be excluded by the presence of the appropriate protocol deviation criterion.

2.2.4 Subgroup of interest

Not applicable.

2.3 Subject Disposition / Demographics / Other Baseline Characteristics

Unless noted otherwise, summaries and listings described in this section will be based on the FAS.

2.3.1 Subject disposition

The following will be tabulated:

- Treatment 1 Disposition/VAY736 Disposition (C1-C6):
 - Number (%) of patients who discontinued treatment with VAY736 and primary reasons for discontinuation
- Treatment 2 Disposition/Ibrutinib Disposition (C1-C9)
 - Number (%) of patients who discontinued treatment with Ibrutinib and primary reasons for discontinuation
- Treatment 3 Disposition/VAY736 Disposition (C7-C9)
 - Number (%) of patients who discontinued treatment with VAY736 and primary reasons for discontinuation
- Post-treatment follow-up
 - Number (%) of patients who discontinued post-treatment follow-up and reasons for discontinuation

2.3.2 Demographic and background data

Demographic data including age, sex, race, ethnicity, height, weight, and ECOG performance status will be listed and summarized. In addition, following age categories will be summarized: 18- <65 years, 65- < 85 years, and \geq 85 years. Additional baseline characteristics data will be included: ibrutinib resistance mutation, the time (in months) from the start of ibrutinib therapy to the first study treatment, and the results of direct and indirect Coombs tests.

2.3.3 Medical History

A listing of medical history and current medical conditions will be provided, using the latest Medical Dictionary for Regulatory Activities (MedDRA) terminology available at the time of reporting.

2.3.4 Prior antineoplastic therapy

All prior antineoplastic medication, radiotherapy and surgery will be listed. The number (%) of patients who received any prior antineoplastic medication will be summarized.

2.3.4.1 Prior antineoplastic medications

The summary of prior antineoplastic medications will include the total number of regimens (note: there can be more than one medication per regimen), setting at last treatment, time (in months) from last treatment to progression, best hematological response per IWCLL at last treatment (defined to be the best response during the last treatment regimens recorded), and reason for discontinuation at last treatment. Prior antineoplastic medications will also be summarized by Anatomical Therapeutic Chemical (ATC) class, and preferred term.

2.3.4.2 Prior antineoplastic radiotherapy

The listing of prior antineoplastic radiotherapy will include the radiotherapy locations, (including all locations recorded for each patient).

2.3.4.3 Prior antineoplastic surgery

Data collected on prior antineoplastic surgery will be listed.

2.3.4.4 Partial-date imputation rules for prior antineoplastic therapies

The following partial-date imputation rules will apply:

Start date:

The same rule which is applied to the imputation of AE/concomitant medication start date will be used, with the exception of the imputation rule in scenario (B) of [Table 2-4](#), which will be replaced by TRTSTD-1. See [Section 2.8.2.1.1](#).

End Date:

Imputed date = min (start date of study treatment, last day of the month), if day is missing;

Imputed date = min (start date of study treatment, 31DEC), if month and day are missing.

If the end date is not missing and the imputed start date is after the end date, use the end date as the imputed start date.

If both the start date and the end date are imputed and if the imputed start date is after the imputed end date, use the imputed end date as the imputation for the start date.

2.3.5 Diagnosis and extent of cancer

The summary and listing of diagnosis and extent of cancer (disease history) will include stage at initial diagnosis, stage at time of study entry, time (in months) since initial diagnosis, time (in months) from initial diagnosis to first relapse, time (in months) since most recent recurrence/relapse, current extent of disease (metastatic sites).

2.4 Protocol deviations

The full list of protocol deviations will be documented in the Study Specification Document (SSD).

2.5 Treatments (study treatment, concomitant therapies, compliance)

2.5.1 Study treatment

The safety set will be used for all summaries and listings of study treatment.

2.5.1.1 Data handling

2.5.1.1.1 Data analysis

Duration of exposure, actual cumulative dose, dose intensity (DI) and relative dose intensity (RDI) will be summarized separately for each component of study treatment in **combination therapy**. The duration of exposure will also be presented for the study treatment (VAY736+ibrutinib). Duration of exposure will be categorized into mutually exclusive time intervals; frequency counts and percentages will be presented for the number (%) of patients in each interval.

The number (%) of patients who have dose reductions or interruptions, and the reasons, will be summarized by treatment.

Patient-level listings of all doses administered on treatment along with dose change reasons will be produced.

2.5.1.2 Duration of exposure to study treatment

Duration of exposure to study treatment refers to exposure to the combination of ibrutinib and the investigational therapy VAY736. The following exposure durations will be calculated:

(A) Duration of exposure to VAY736 (*days*) = (last date of exposure to VAY736) – (date of first administration of VAY736) + 1

(B) Duration of exposure to ibrutinib (*days*) = (last date of exposure to ibrutinib) – (date of first administration of ibrutinib) + 1

(C) Duration of exposure to study treatment (days) = $\max(\text{last date of exposure to ibrutinib or VAY736}) - (\text{date of first administration of ibrutinib}) + 1$ will be used for the duration of exposure to study treatment

The last date of exposure to ibrutinib is the last date of dose administration.

The last date of exposure to VAY736 administered Q2W is the last date of administration +13 days.

The last date of exposure to VAY736 administered Q4W is the last date of administration +27 days.

Table 2-2 Definition of last date of exposure of investigational drug

Scenario	Definition of last date of exposure of investigational drug	Example
Scenario 1: Investigational drug with a cyclic administration	
The planned end date of the last cycle in which the last non-zero dose of the investigational drug was last administered.
 
Note: If the patient died or was lost to follow-up before the derived last date, the last date of exposure to investigational drug is the date of death or the date of last contact, respectively.
 
If the derived last date of exposure goes beyond the data cutoff date, it should be truncated to the date of data cutoff.
	
Example 1: In a once-a-week administration of an investigational drug, the last date of exposure is the date of administration in the last cycle + 6 days.
 
Example 2: In a 21-day cycle with one or several infusions in the beginning of the cycle (e.g., 2 weeks on 1 week off), the last date of exposure is the date of first infusion in the last cycle + 20 days.

Scenario 2: Daily administration of the investigational drug	Date of last administration of a non-zero dose of the investigational drug.	
Example 3: A patient had a permanent discontinuation of the investigational drug 06-Jan-2013 after being put on a temporary interruption since 01-Jan-2013. In this case the last date of exposure is 31-Dec-2012.

2.5.1.3 Cumulative dose

Cumulative dose of a study treatment is defined as the total dose given during the study treatment exposure and will be summarized for each of the study treatment components, VAY736 and ibrutinib, respectively.

The **planned cumulative dose** for a study treatment component refers to the total planned dose as per the protocol up to the last date of investigational drug administration. The planned cumulative dose is not summarized/listed. It is used for relative dose intensity calculations.

The **actual cumulative dose** refers to the total actual dose administered, over the duration for which the patient is on the study treatment. For VAY736, this is documented in the VAY736 Dose Administration eCRF.

For ibrutinib, **the planned and actual dose** is the first non-zero dose as recorded on the Study treatment – PK - Ibrutinib eCRF. Any periods of dose interruption or reduction are be recorded in the change log.

For patients who did not take any drug, the actual cumulative dose is equal to zero for that drug.

For VAY736, the actual cumulative dose is the sum of the non-zero doses recorded over the dosing period, and the planned cumulative dose is the planned starting dose summed over the same dosing period.

For ibrutinib, the actual cumulative dose is calculated as the planned dose, multiplied by the duration of exposure to ibrutinib, accounting for any periods of dose interruptions. The planned cumulative dose is the dose is calculated as the planned dose multiplied by duration of exposure to ibrutinib.

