1.2 Study objectives and endpoints

Objectives and related endpoints are described in [Table 1-1](#) below.

Table 1-1 Objectives and related endpoints

Objective	Endpoint	Analysis
Primary		Refer to Section 2.6
To determine the MTD and/or RD of the combination of VAY736 with ibrutinib	Safety Escalation only: 
Incidence of DLTs in cycle 1 (28 days)	
To characterize the safety and tolerability of the combination of VAY736 and ibrutinib	Escalation and expansion: 
Incidence and severity of AEs and SAEs, including changes in laboratory parameters and vital signs Tolerability Dose interruptions, reduction, and dose intensity	
Secondary		Refer to Section 2.8
To assess any preliminary antitumor activity of the combination	Rate of patients with CR/CRI assessed by investigators per IWCLL at cycle 9 day 1 Overall response rate (ORR) assessed by investigators per IWCLL criteria and Time To Progression (TTP)	
	Clearance of ibrutinib resistance mutations (BTKC481 and/or PCLy2 hotspot), defined as less than 1% mutation bearing alleles (Arm B only).	
To characterize the PK of VAY736 and ibrutinib when used in combination therapy	Plasma concentration of VAY736 and ibrutinib, and derived parameters	
To assess immunogenicity (IG) following one or more intravenous infusions of VAY736	Presence of anti-VAY736 antibodies	

Objective	Endpoint	Analysis

2 Statistical methods

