2.5.1.5 Dose reductions, interruptions, or permanent discontinuations

The number of patients who have dose reductions or interruptions, and the reasons, will be summarized separately for each of the study treatment components.

‘Dose interrupted’ and ‘Dose changed’ fields from the Dosage Administration CRF pages (DAR) will be used to determine the dose interruptions and dose changes, respectively.

Dose reduction: a dose change where the prescribed dose level is lower than the previous prescribed dose level or where the actual dose administered is lower than the prescribed dose. Only dose change is collected in the CRF, number of reductions will be derived programmatically based on dose change flag and the change and the direction of the change. Dose reduction will be reported for VAY736 only.

Dose interruption: Actual dose administered equal to zero, between the first and last non-zero doses, following a non-zero actual dose administered. Dose interruption is collected as such in the treatment page eCRF. Number of dose interruptions and corresponding reason will be summarized.

- For VAY736, ‘Dose interrupted’ field from the Dosage Administration CRF pages (DAR) will be used to determine the dose interruptions.
- For ibrutinib, dose interruptions will be captured in the dose change log.

The corresponding fields ‘Reason for dose change/dose interrupted’ will be used to summarize the reasons. For the purpose of summarizing interruptions and reasons, in case multiple entries for interruption that are entered on consecutive doses with different reasons, they will be counted as separate interruptions. However, if the reason is the same in these mentioned multiple entries on consecutive doses, then it will be counted as one interruption.

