2.5.3 Compliance

Compliance to the study treatment will be summarized in terms of the RDI. The predefined RDI categories are < 0.5 , $\geq 0.5 - < 0.75$, $\geq 0.75 - < 0.9$, $\geq 0.9 - < 1.1$ and ≥ 1.1 . The number and proportion of patients falling in each category will be presented.

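### Ibrutinib dose intensity and RDI-based compliance ignore dose reductions, and the count of reductions leaves ibrutinib out

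*SAP*

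**What the plan says.** For ibrutinib, SAP 2.5.1.3 uses one value per patient, the first non-zero recorded dose, as both planned and actual dose. Planned cumulative dose is that value times the duration of exposure. Actual cumulative dose is "calculated as the planned dose, multiplied by the duration of exposure to ibrutinib, accounting for any periods of dose interruptions". The same section states that "Any periods of dose interruption or reduction are be recorded in the change log", and its general definition says that actual cumulative dose "refers to the total actual dose administered, over the duration for which the patient is on the study treatment". For VAY736 the rule differs: the recorded doses are summed.

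SAP 2.5.1.4 divides cumulative dose by duration to get DI and planned DI, and takes their ratio as RDI. Under SAP 2.5.3, "Compliance to the study treatment will be summarized in terms of the RDI", in bands cut at 0.5, 0.75, 0.9 and 1.1.

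On counting reductions, SAP 2.5.1.5 opens with "The number of patients who have dose reductions or interruptions, and the reasons, will be summarized separately for each of the study treatment components" and later says "Dose reduction will be reported for VAY736 only". SAP 2.5.1.1.1 says that the number of "patients who have dose reductions or interruptions, and the reasons, will be summarized by treatment".

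The primary tolerability endpoint in SAP Table 1-1 is "Dose interruptions, reduction, and dose intensity". Protocol 10.3 bases dose intensity for both drugs on the cumulative dose actually received, and asks for counts of patients with reductions without excluding either drug. Protocol 6.3.1.2 foresees ibrutinib reductions in patients who do not tolerate it.

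**The concern.** The ibrutinib formula adjusts for interruptions and for nothing else, although the SAP says reductions are recorded. A patient whose ibrutinib dose is cut during the study, with no days missed, is reported as having received the full dose. The sentence restricting reductions to VAY736 removes the one summary count that would have shown it.

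The SAP defines ibrutinib as a study drug (2.1.1.1), and reductions and dose intensity are named parts of the primary endpoint in both study parts. For any affected patient the error runs one way, towards better apparent tolerability of the combination. The rule also treats equal losses of drug unequally: loss through interruption lowers RDI, while loss through reduction does not.

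**Working it through.** The documents give no numerical result on this point, so there is no figure to reproduce. The SAP formulas are applied directly.

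**Algebra.** Let d be the first non-zero dose, T the duration of exposure in days and I the interrupted days.

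- Actual cumulative dose (SAP 2.5.1.3) = d × (T − I)
- Planned cumulative dose (SAP 2.5.1.3) = d × T
- DI and planned DI are divided by the same duration (SAP 2.5.1.4), which cancels: RDI = d(T − I) / (dT) = 1 − I/T

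No reduced dose appears, and ibrutinib RDI can never exceed 1.

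**Inputs for an illustration.** d = 420 mg, the dose required in escalation (Protocol 5.2). T = 8 cycles × 28 days = 224 days, ibrutinib running through C8D28 (Protocol 4.1). Planned cumulative dose = 420 × 224 = 94,080 mg. The reduced doses (two thirds and one third of 420 mg, that is 280 and 140 mg) and their timing are assumptions for arithmetic only. No interruption, so I = 0.

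| Reduction (assumed) | Dose given, mg | RDI from dose given | RDI by SAP rule |
|---|---|---|---|
| 280 mg from day 57 (168 days) | 56×420 + 168×280 = 70,560 | 0.750 | 1.00 |
| 140 mg from day 57 (168 days) | 56×420 + 168×140 = 47,040 | 0.500 | 1.00 |
| 280 mg from day 169 (56 days) | 168×420 + 56×280 = 86,240 | 0.917 | 1.00 |
| 140 mg from day 169 (56 days) | 168×420 + 56×140 = 78,400 | 0.833 | 1.00 |

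**Equal loss, unequal result.** A 56-day interruption loses 56 × 420 = 23,520 mg, and the SAP rule gives 1 − 56/224 = 0.75. A period of 168 days at 280 mg loses 168 × 140 = 23,520 mg, and the SAP rule gives 1.00.

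**When the compliance band is wrong.** With no interruption the SAP rule always places the patient in the band from 0.9 to below 1.1. With r days at a fraction f of the dose, the true RDI is 1 − (1 − f)r/224. It falls below 0.9 once r > 0.1 × 224/(1 − f):

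- f = 2/3: r > 67.2, so from 68 days
- f = 1/3: r > 33.6, so from 34 days

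Shorter reductions leave the band unchanged, but cumulative dose, DI and RDI are still overstated.

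**Text against text.** Within SAP 2.5.1.3, the general definition asks for the dose administered and the ibrutinib formula does not deliver it. Within SAP 2.5.1.5, reductions are promised for each component and then confined to VAY736. Against Protocol 10.3, both the basis for dose intensity and the unrestricted count of reductions are departed from. Protocol 10.5.3.6 likewise assesses tolerability through reductions without naming only one drug. The readable items of SAP Section 4, which declare changes as small as the vomiting window and the ECG listing, do not mention this one.

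**The case against.** There are four fair points on the other side.

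- **Reading of SAP 2.5.1.1.1.** SAP 2.1 defines a treatment as a combination of VAY736 and ibrutinib doses plus regimen. Summarizing reductions by treatment may therefore name the table column and not promise a count per drug. That makes this conflict weaker than the others, but a count for the combination should still include a patient whose only reduction was of ibrutinib.
- **Incomplete drafting.** The cumulative-dose sentence may simply have left reductions out, and the separate programming specifications, which are not available here, may supply them. That is possible for the formula. It does not explain the explicit restriction of reduction reporting to VAY736.
- **Other outputs.** SAP 2.5.1.1.1 commits to patient-level listings of all doses with reasons for change, and the adverse-event overview (SAP 2.8.2.1.2) includes dose reductions and interruptions without restriction by drug. In escalation, a reduction caused by an adverse event in cycle 1 would also count as a DLT. These help a reader find individual cases. They do not correct a wrong DI, RDI or compliance table.
- **Few patients.** Protocol 1.2.4.1.2 cites adverse reactions leading to ibrutinib reduction in about 6% of patients. If that applied here, 0.06 × 26 ≈ 1.6 of the 15 escalation and 11 expansion patients reported at Amendment 06 would be affected, or 0.06 × 60 = 3.6 of the largest planned enrolment (20 + 40). Patients must already be tolerating ibrutinib at entry, which may lower the rate; the 6% is not for this combination, so it is indicative only. Those entering expansion on a stable lower dose are unaffected, because that dose is their planned dose.

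The summaries are also descriptive, in an open-label Phase Ib trial that was endorsed for early termination for business reasons. This limits the consequence but does not make the derived values right.

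**Conclusion.** The point holds. As the SAP stands, ibrutinib RDI equals 1 − I/T whatever dose the patient was taking, and ibrutinib reductions are not counted. For an affected patient the overstatement ranges from 0.08 (0.917 reported as 1.00) to 0.50 (0.500 reported as 1.00) in the assumed scenarios, always in the favourable direction. The size for a real patient depends on the depth and length of the reduction. The documents give no reduction rate for this combination, so the number of affected patients cannot be established from them.

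The scope is limited to the exposure, dose-intensity, reduction and compliance summaries. DLT rates, the Bayesian logistic regression model, the MTD or recommended dose and the efficacy analyses do not use ibrutinib RDI. Because named parts of the primary tolerability endpoint would be wrong, it should be fixed. Confidence in the reading of the text is high.

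**What to change.** 1. In SAP 2.5.1.3, define ibrutinib actual cumulative dose as the sum over days of the daily dose in force according to the change log, with zero on interrupted days. Keep planned cumulative dose as starting dose times duration. DI, RDI and the compliance bands then follow without further change.
2. In SAP 2.5.1.5, delete "Dose reduction will be reported for VAY736 only" and tabulate ibrutinib reductions, with reasons where these were recorded.
3. First check whether the change log holds the reduced daily dose and the reason. If it does not, declare the departure from Protocol 10.3 in SAP Section 4, and label ibrutinib cumulative dose, DI, RDI and compliance as reflecting interruptions only.

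The cost is SAP wording and some programming, by amendment before database lock or addendum after it (SAP Section 1). The fallback costs text only. No new data collection is proposed. Ibrutinib RDI may look less favourable as a result.

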2.5.1.4 Dose intensity and relative dose intensity

Dose intensity (DI) for patients with non-zero duration of exposure is defined as follows:

$DI \text{ (dosing unit / unit of time)} = \text{Actual Cumulative dose (dosing unit)} / \text{Duration of exposure (unit of time)}$

For example, the dosing unit for VAY736 is mg/kg and the unit of time is 14 days:

$$\begin{aligned} DI \text{ (mg/kg/14 days)} &= 14 * \text{Actual Cumulative dose (mg/kg)} / \text{Actual duration of exposure} \\ &= 14 * \text{Actual cumulative dose (mg/kg)} / [\text{Last dosing date} - \text{First dosing date} + \text{Dose interval (14 days)}] \end{aligned}$$

For Ibrutinib the dosing unit is mg, and the unit of time is day (mg/day):

$$\begin{aligned} DI \text{ (mg/day)} &= \text{Actual Cumulative dose (mg)} / \text{Actual duration of exposure (day)} \\ &= \text{Actual cumulative dose (mg)} / [\text{Last dosing date} - \text{First dosing date} + \text{Dose interval (1 day)}] \end{aligned}$$

For patients who did not take any drug the DI is by definition equal to zero.

Planned dose intensity (PDI) is defined as follows:

$$PDI \text{ (dosing unit / unit of time)} = \text{Planned Cumulative dose (dosing unit)} / \text{Duration of exposure (unit of time)}$$

For example, the dosing unit for VAY736 is mg/kg and the unit of time is 14 days:

$$DI \text{ (mg/kg/14 days)} = 14 * \text{Planned Cumulative dose (mg/kg)} / \text{Duration of exposure}$$

For Ibrutinib the dosing unit is mg, and the unit of time is day (mg/day):

$$DI \text{ (mg/day)} = \text{Planned Cumulative dose (mg)} / \text{Duration of exposure (day)}$$

Relative dose intensity (RDI) is defined as follows:

$$RDI = DI \text{ (dosing unit / unit of time)} / PDI \text{ (dosing unit / unit of time)}.$$

As an example, the RDI for VAY736 is defined as:

$$RDI = DI \text{ (mg/kg/14 days)} / PDI \text{ (mg/kg/14 days)}$$

DI and RDI will be summarized separately for each of the study treatment components, using the duration of exposure of each of the components. The duration of exposure considered for the derivation of the DI and the RDI will be derived from the start date of study treatment to the end of the last cycle initiated irrespective of date of death, last contact date for withdraw consent and cut-off date.

RDI will be summarized as a percentage. Summary of RDI may include categorical summaries, based on clinically meaningful intervals; see SAP [Section 2.5.3](#).

